### *Study Subjects*

#### Inclusion Criteria:

- Twin gestation
- Scheduled cesarean delivery ( $\geq 34$  weeks)

#### Exclusion criteria for methylergonovine:

- Subjects with known hypertensive disease: history of chronic hypertension, gestational hypertension or preeclampsia with or without severe features
- Use of protease inhibitors given known vasoconstrictive side effects with concomitant methylergonovine administration

- Hypersensitivity to methylergonovine or any of the ingredients

If patients meet any of the exclusions above, they will be assessed for the use of Hemabate and excluded if:

- Subjects with known asthma disease
- Hypersensitivity to Hemabate or any of the ingredients

Additionally, if subjects meet any of the following criteria, they will be excluded from participation:

- Participating in another intervention study where the primary outcome includes postpartum bleeding or thromboembolism, or the study intervention directly affects postpartum bleeding or thromboembolism
- Receipt of uterotonics, other than oxytocin, or planned or expected use of uterotonic prophylaxis
- Non-elective cesarean delivery

## STATISTICAL ANALYSIS

Based on the following parameters, the sample size was calculated for the primary outcome of mean hemoglobin change from pre-op to post-op day 1 between placebo and treatment groups. The analysis was conducted in Stata 17. From the protocol: Based on a prior study of cesarean deliveries in twin gestations [9], a mean (SD) change in hemoglobin level for elective cesarean delivery of 1.40 (0.83) g/dL was estimated. Up to 20% crossover rate from the treatment group to the placebo group will be assumed. Because there is no accepted definition of a minimum clinically important difference in postoperative hemoglobin change, effect size was based on the published SD of the mean. Given the burden of maternal morbidity and mortality due to postpartum hemorrhage, the investigators decided that even a 1-SD greater drop in postoperative maternal hemoglobin level with Methylergonovine treatment arm might alter clinical decision-making. Hence the parameters are as follows:

Effect size / difference in means: 0.83SD: 0.83 (assumed to be the same for both groups)

Allocation ratio: 1:1

Crossover rate: 20%

Power: 0.90

Alpha: 0.05 (two-tailed)

Assumed dropout rate: 10%

The sample size is 33 per group, or 66 total on the more conservative end, including adjustment for potential loss to follow up.

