## BACKGROUND

### *Study Purpose and Rationale*

Obstetrical hemorrhage is a leading cause of maternal morbidity and mortality worldwide with a significantly higher frequency and severity following cesarean delivery. In 2020, 31.9 percent of pregnant women in the United States underwent cesarean delivery, [1] making it the second most common operation performed. Though multiple complications can occur following cesarean delivery, hemorrhage morbidities are among the most common with significant cardiovascular implications [2]. Twin gestations are at particularly higher risk for postpartum hemorrhage due to impaired myometrial contractility and atony following overdistention; increased maternal blood volume; and increased uterine blood flow compared to singletons, yet the management of obstetrical bleeding following twin delivery remains identical to singleton delivery [3]. Current strategies to address intrapartum hemorrhage have relied on pharmacological and mechanical treatments after intraoperative identification. However, there is extensive work on prophylactic therapies administered intraoperatively to prevent obstetrical hemorrhage [4-6]. Recent evidence has emerged about the utility of prophylactic Methylergonovine for the prevention of obstetrical hemorrhage [7-8]. Methylergonovine, a semisynthetic ergot alkaloid, acts primarily on alphaadrenergic receptors of uterine and vascular smooth muscle, increasing uterine tone and promoting vasoconstriction. Masse et al [8] in a randomized trial of 80 women undergoing intrapartum cesarean delivery found that fewer patients who were allocated to the methylergonovine group received additional uterotonic agents (20% vs 55%, relative risk [RR] 0.4, 95% CI 0.2–0.6). Participants receiving methylergonovine were more likely to have satisfactory uterine tone (80% vs 41%, RR 1.9, 95% CI 1.5–2.6), lower incidence of postpartum hemorrhage (35% vs 59%, RR 0.6, 95% CI 0.4–0.9), lower mean quantitative blood loss (967 mL vs 1,315 mL; mean difference 348, 95% CI 124–572), and a lower frequency of blood transfusion (5% vs 23%, RR 0.2, 95% CI 0.1–0.6). Investigators concluded that the administration of prophylactic methylergonovine in addition to oxytocin in patients undergoing intrapartum cesarean birth reduces the need for additional uterotonic agents. Similarly, Senturk et al [7], in a prospective study of 1210 participants found that intraoperative, prophylactic methylergonovine decreased post-operative blood loss with no adverse side effects. Randomized trials of Methylergonovine as prophylaxis to prevent hemorrhage in cesarean

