## RESEARCH AIMS & ABSTRACTS

*Research Question(s)/Hypothesis(es):* To evaluate whether prophylactic uterotonic therapy reduces maternal blood loss among individuals with twin gestations undergoing cesarean delivery.

*Primary Research Question:* Is the administration of prophylactic uterotonic therapy at the time of scheduled cesarean delivery after cord clamping of the second twin associated with decreased maternal blood loss among patients with twin pregnancies (based on primary outcome of maternal hemoglobin drop from preop to postoperative day #1)?

*Hypothesis:* Prophylactic uterotonic therapy in cesarean delivery among patients with twin pregnancies is associated with decreased maternal blood loss compared to placebo.

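### Does justifying the target difference as a greater hemoglobin drop on methylergonovine undermine the sample size or the reading of the result?

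*Combined protocol and SAP*

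**What the plan says.** The hypothesis in RESEARCH AIMS & ABSTRACTS is that "Prophylactic uterotonic therapy in cesarean delivery among patients with twin pregnancies is associated with decreased maternal blood loss compared to placebo". BACKGROUND, the Scientific Abstract and STUDY DESIGN state the same direction.

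STATISTICAL ANALYSIS sizes the trial on "the primary outcome of mean hemoglobin change from pre-op to post-op day 1 between placebo and treatment groups". It takes its reference values from a prior study: "a mean (SD) change in hemoglobin level for elective cesarean delivery of 1.40 (0.83) g/dL was estimated". It says that no minimum clinically important difference is accepted for this outcome, and that therefore "effect size was based on the published SD of the mean". The next sentence adds the clinical gloss, that "even a 1-SD greater drop in postoperative maternal hemoglobin level with Methylergonovine treatment arm might alter clinical decision-making". The listed inputs are "Effect size / difference in means: 0.83SD: 0.83 (assumed to be the same for both groups"), "Alpha: 0.05 (two-tailed"), power 0.90, 1:1 allocation, 20% crossover and 10% dropout. The result is 33 per group, 66 in total.

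Study Purpose and Rationale describes a randomized trial of 80 women having intrapartum cesarean delivery, which found "lower mean quantitative blood loss (967 mL vs 1,315 mL; mean difference 348", with a 95% CI of 124 to 572 mL.

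**The concern.** The sentence that gives the target its clinical meaning points the wrong way. Taken literally, it sets a threshold for harm (the drop rising from 1.40 to 2.23 g/dL on treatment) in a trial that asks about benefit. A sample size whose stated rationale does not match its hypothesis invites the question of whether the calculation answers the trial's question at all.

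Turning the sentence round raises a second worry. A benefit of 0.83 g/dL removes 59% of the reference drop, yet the wording presents one SD as a modest amount. The only mean blood-loss effect quantified in the documents is a 26.5% reduction. If the real effect on hemoglobin were of that relative size, the trial would more likely than not miss significance, and a reader relying on this sentence might take a null result as evidence that the drug does nothing useful.

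**Working it through.** **Inputs.** From STATISTICAL ANALYSIS: reference drop 1.40 g/dL, SD 0.83, target difference 0.83, two-sided alpha 0.05, power 0.90, crossover 20%, dropout 10%. From Study Purpose and Rationale: mean blood loss 967 vs 1,315 mL, difference 348 mL (95% CI 124 to 572).

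**1. The plan's figure.** The normal approximation gives n per group = 2 × (1.960 + 1.282)² × (0.83/0.83)² = 21.01, rounded up to 22. The t-test needs 22.02, so 23. Then 23/0.8 = 28.75, so 29 for crossover, and 29/0.9 = 32.2, so 33 for dropout. This reproduces the stated 33. (Diluting the effect by crossover to 0.664 g/dL also gives 33 by the normal formula, but without a dropout allowance; adding one gives 37. That is a separate matter from direction.)

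**2. Does the direction matter?** The difference enters the formula squared and the test is two-sided. With +0.83 or −0.83 the normal formula gives 22 before allowances and the t-test 23. Only the implied treated mean changes:

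| Reading | Treated drop | Change from 1.40 |
|---|---|---|
| As worded | 1.40 + 0.83 = 2.23 g/dL | 59% larger |
| As hypothesised | 1.40 − 0.83 = 0.57 g/dL | 59% smaller |

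**3. How large is the target beside the cited effect?** 0.83/1.40 = 59.3% and 348/1,315 = 26.5%; the ratio is 2.24. With the plan's 20% crossover the expected difference is 0.8 × 0.83 = 0.664 g/dL, which is 47.4% of 1.40, and the ratio falls to 1.79. The cited interval is 124/1,315 = 9.4% to 572/1,315 = 43.5%.

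**4. Power if hemoglobin drop scaled with blood loss (an assumption).** Two-sided t-test, SD 0.83, 33 × 0.9 = 29.7, so about 30 evaluable per arm:

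| Relative reduction | Effect on 1.40 g/dL | Power, no crossover | Power, 20% crossover |
|---|---|---|---|
| 9.4% (lower limit) | 0.13 | 9% | 8% |
| 26.5% (estimate) | 0.37 | 40% | 27% |
| 43.5% (upper limit) | 0.61 | 80% | 61% |

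**5. What could a null result exclude?** The 95% CI half-width is t(58, 0.975) × 0.83 × √(2/30) = 0.43 g/dL. An observed difference of zero would exclude benefits above 0.43 g/dL, which is 0.43/1.40 = 31% of the reference drop and 0.43/0.83 = 52% of the target.

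**The case for a change.** The strongest case for a change runs as follows. The contradiction is in current, complete text and is not an artefact of extraction. The plan offers no argument that 0.83 g/dL is achievable, and even the upper limit of the cited blood-loss interval (43.5%) lies below both 59% and the crossover-diluted 47%. At the cited point estimate, power is 27% to 40%. The plan has no rule for interpreting a non-significant result. Rewording the sentence and adding such a rule would cost no patients.

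Much of this stands as description. The wording is wrong, the target is large, and its plausibility is not argued. The step to a required change fails on three points.

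- The misworded sentence is not the sole basis for the target. The sentence before it openly ties the effect size to the published SD for want of an accepted threshold, and that basis has no direction. One may think one SD optimistic, but the choice is disclosed.
- The comparison with the cited trial crosses outcome (mL against g/dL), setting (intrapartum against scheduled) and population (BACKGROUND says that trial excluded twins). The choice of comparator also matters: the same trial's binary outcomes show relative reductions of 41% for hemorrhage (1 − 35/59), 64% for additional uterotonics (1 − 20/55) and 78% for transfusion (1 − 5/23). Those are no better as proxies for a mean hemoglobin change, but they show that the documents contain no single cited effect to plan against. Mean blood loss is the nearest analogue, and its own interval leaves power anywhere from 9% to 80% before crossover.
- No section commits the investigators to reading a non-significant result as absence of benefit. By step 5 a null estimate would also exclude benefits larger than about half the target, so the trial is not confined to ruling out only extreme effects.

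**Conclusion.** No change is needed. The phrase about a greater drop is a clerical slip: the hypothesis is stated correctly in four other places, the test is two-sided, and the sample size, the test and the estimate are the same under either sign. Any analyst will read it as a 0.83 g/dL smaller drop on prophylaxis.

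The size of the target, 59% of the reference drop (47% after crossover), is a disclosed planning choice made without an accepted threshold. Low power at a smaller effect does not show that the plan misses its stated 90% at 0.83 g/dL. The figures of 27% to 40% hold only if hemoglobin drop scales in proportion to blood loss across different outcomes and populations, which the documents do not support. Adding them to the protocol would suggest a precision that the evidence lacks. Reporting the difference with its 95% CI, as analysts ordinarily do, lets readers judge a null result without a special rule.

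### With 20% crossover analysed as randomised and 10% dropout, 33 per group gives about 86–87% power, not the stated 90%

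*Combined protocol and SAP*

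**What the plan says.** The whole calculation is in the Statistical Analysis section of the combined protocol and SAP. The primary outcome is the change in hemoglobin from before surgery to postoperative day 1. The variability comes from a published study: "a mean (SD) change in hemoglobin level for elective cesarean delivery of 1.40 (0.83) g/dL was estimated". The target difference is set at one SD, so the difference and the SD are both 0.83 g/dL, with the SD "assumed to be the same for both groups". Allocation is 1:1, power 0.90 and alpha 0.05 two-tailed.

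Two allowances are listed separately. Non-adherence is in one direction: "Up to 20% crossover rate from the treatment group to the placebo group will be assumed". The parameter list then fixes that rate at 20% and adds a 10% dropout rate. The conclusion is: "The sample size is 33 per group, or 66 total on the more conservative end, including adjustment for potential loss to follow up".

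No formula, intermediate sample size or order of adjustments is given. The documents do not name an analysis population or say how patients who cross over will be analysed.

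**The concern.** Crossover and dropout act differently on power. A dropout removes an observation. A patient assigned to treatment who does not receive it, and who is analysed as randomised, still contributes an observation, but one without the treatment effect, so the expected difference between arms shrinks. Because the required size varies with the inverse square of the difference, 20% crossover costs more than a 20% loss of patients: the multiplier is 1/0.8² = 1.56 rather than 1/0.8 = 1.25.

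The figure of 33 is what the normal formula gives for crossover alone, before any dropout, which suggested that one allowance was missing or had been applied in a way that does not protect the randomised comparison. At stake is whether the trial has the 90% power that the section presents as holding after both allowances. With no working shown, a reader cannot tell.

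**Working it through.** **Inputs** (all from the Statistical Analysis section): difference 0.83 g/dL; SD 0.83 g/dL in both arms; 1:1 allocation; two-sided alpha 0.05; power 0.90; crossover 20%, treatment to placebo; dropout 10%. Assumption added here: crossovers are analysed in their assigned group.

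**Formula.** Per group, n = 2(z₀.₉₇₅ + z₀.₉₀)²/d², where d is the difference divided by the SD and z₀.₉₇₅ + z₀.₉₀ = 1.960 + 1.2816 = 3.2415. The t-test sizes use the noncentral t distribution. Dropout is applied as n/(1 − 0.10).

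**Reproducing the stated 33.** Three routes reach it:

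1. Crossover as dilution, no dropout: d = 0.8, n = 2 × 3.2415²/0.64 = 32.84, rounded up to 33 (normal).
2. Crossovers counted as lost patients, with dropout: the t-test size at d = 1 is 22.02, rounded up to 23; 23/0.8 = 28.75, up to 29; 29/0.9 = 32.2, up to 33.
3. The two rates added as a 30% loss: 23/0.70 = 32.9, up to 33.

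Dropout alone with no crossover gives 25 (normal) or 26 (t), so crossover must have entered in some form. The plan does not show which route was used.

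**Size that meets the listed inputs, analysed as randomised.** The diluted difference is 0.8 × 0.83 = 0.664 g/dL, so d = 0.664/0.83 = 0.8.

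| | Normal | t test |
|---|---|---|
| Evaluable per group | 32.84 → 33 | 33.83 → 34 |
| Randomised per group, 10% dropout | 33/0.9 = 36.7 → 37 | 34/0.9 = 37.8 → 38 |
| Total | 74 | 76 |

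**Power of the stated size.** With 33 randomised per group, 33 × 0.9 = 29.7 are evaluable, about 30. At d = 0.8:

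| Evaluable per group | Normal | t test |
|---|---|---|
| 29.7 | 86.9% | 85.8% |
| 30 | 87.3% | 86.1% |
| 33 (no dropout) | 90.1% | 89.3% |

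A simulation with equal SDs, 30 per group and 200,000 runs gave 86.1%, matching the t-test figure.

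**Dependence on crossover** (t test, 30 evaluable per group):

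| Crossover | d | Power |
|---|---|---|
| 5% | 0.95 | 95.1% |
| 10% | 0.90 | 92.9% |
| 15% | 0.85 | 89.9% |
| 20% | 0.80 | 86.1% |

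Power is exactly 90% at 14.4% crossover with 29.7 evaluable, or 14.9% with 30. At 20% crossover and 30 evaluable, the full-treatment difference detectable with 90% power is 0.883 g/dL rather than 0.83.

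**Beyond the plan's assumptions.** If crossovers and non-crossovers differ by the full 0.83, mixing them widens the treatment-arm variance by 1 + 0.8 × 0.2 = 1.16, and power falls to about 83%. The plan assumes equal SDs, so this is not part of the main figure.

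**The case against.** The strongest reply is that 33 is not a slip. Routes 2 and 3 above reach it with dropout included, so the statement that loss to follow-up is covered may be literally accurate. The plan also never says that crossovers are analysed as randomised; that condition is mine. If crossovers were excluded and the full effect held in the rest, about 24 against 30 patients would remain and power would be about 95%.

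This stands in part. The cause cannot be established, and it should not be called a proven miscalculation. But the choice of route does not rescue the power claim. Patients who cross over remain in the treatment arm of a randomised comparison and dilute it, however the 33 was reached. Nothing in the documents provides for excluding or reassigning them, and crossover is listed separately from dropout. That the same 66 patients could mean 86% or 95% power is itself a reason to state the handling.

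Second, the text describes 20% as a ceiling, and 10% loss may be cautious for a routine day-1 blood count. Both points soften the practical effect: with no loss, power at 20% crossover is 89–90%. But the parameter list fixes both rates, and a size described as conservative should hold at them.

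Third, the shortfall is small beside the uncertainty in the SD. With 30 per group and 20% crossover, an SD of 0.78 restores 90% power, while 0.90 lowers it to 80%. That is true and limits the seriousness, but it works in both directions and does not make the stated figure correct.

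**Conclusion.** The concern holds. On the plan's own inputs, with crossovers kept in their assigned arm, 33 randomised per group delivers about 86% (t) or 87% (normal) power rather than 90%. The shortfall is 3–4 percentage points, equivalent to 4–5 patients per group or 8–10 in total. The 90% claim holds only while crossover stays at or below about 14–15% (t test).

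The conclusion rests on as-randomised analysis, one-way crossover at the listed 20%, dropout at the listed 10% and equal SDs. It does not bias the treatment estimate or invalidate the test. It should be corrected because the stated power is not what the design gives at its listed values, and the text gives no means of seeing that.

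**What to change.** Revise the sample-size paragraph in the Statistical Analysis section to:

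- give the formula (normal or t), the size at each step and how crossover enters;
- name the primary analysis population and say how crossovers are analysed, since the power depends on it;
- replace the 90% claim with a statement that is true whichever route produced 33. Suggested wording: *With 66 randomised and 10% loss (about 30 evaluable per group), power for the comparison as randomised, with crossovers kept in their assigned group, is about 86% at 20% crossover and at least about 90% if crossover is 14% or less.*

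This costs one paragraph and no extra patients; the only downside is a slightly less favourable stated power. If 90% power at 20% crossover is to remain the claim, the stated size must be 37–38 per group (74–76 total), which is 8–10 more patients than now.
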